7.3 Study Schedule

7.3.1 Screening

Screening will occur with support from DataCore/MCIT

- Obtain list of potential participants in NYU Langone Health System
- Review list of potential participants to identify those with upcoming clinical visits (during Q2-3 of 2022)
- Review potential participant charts to confirm likely eligibility
- Message eligible participants' providers to coordinate staff visit at clinical appointment
- MyChart messages will be used to contact potential research participants.

7.4 Enrollment/Baseline

Enrollment/Baseline Visit (Visit 1)

- Verify inclusion/exclusion criteria
- Answer questions from potential participants regarding the air monitors, PACs and BP monitors to verify interest in participating
- Obtain written consent from eligible participant
- Schedule study visits (video visit for setup and clinical visit 2 for second blood draw) for individuals who are eligible and available to participate for the full duration of the study
- Record participant BP, height, weight, and waist circumference if not done as part of clinical visit
- Collect blood for baseline biomarker measurement pre-intervention: <15 mL for all, additional ~10 mL for participants opting into future research.

7.5 Video Visit

Video visit for equipment setup

- Conduct video visit at a mutually agreeable time to instruct participants in equipment setup
 - Place PAC in an acceptable location in bedroom with recommended air space surrounding PAC, and PAC plugged into electricity monitor
 - Place PM monitor in an acceptable location in bedroom with adequate space between PAC and PM monitor to ensure representative sample
 - Connect PM monitor to WiFi if available
- Supervise participant self-measuring BP once to ensure real-time data transmission
- PAC must be turned on ≤7 days from baseline blood draw (Visit 1)

7.6 Final Study Visit

Final Study Visit (Visit 2: 4 weeks after PAC turned on)

- Participants return study equipment: PM monitors, BP monitor data hubs, electricity monitors
- Collect blood for post-intervention biomarker measurement: <15 mL for all, additional ~10 mL for participants opting into future research.
- Final blood draw must occur ≤35 days from turning on PAC

7.7 Withdrawal Visit

Subjects may withdraw from the study at any time and visit will be scheduled to return any study equipment that has been received (PM monitors, BP monitor data hubs, electricity monitors). No withdrawal visit is required for withdrawal from future research.

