4.1 Description of Study Design

In this research, we will conduct a randomized, double-blind, sham-controlled pilot trial to study the effect of PAC use on the concentrations of circulating biomarkers of inflammation in outpatient adults within the NYU Langone Health system.

Aim 1: To determine if 4 weeks of home air filtration with PACs compared to sham is associated with significant reductions in TNF α concentrations when measured before and after intervention.

Data collection will begin Q2 2022 with a total of two time points 4 weeks apart, pre- and post-intervention. The study design utilizes purposeful selection of 74 adults with stable hypertension within the NYU Langone health system outpatient cohort. We will define stable hypertension as no medication changes in prior 30 days, systolic BP <160 mm Hg and either \geq 130 mm Hg without antihypertensive medications, or diagnosis of hypertension in medical records. Per guidelines, this range is considered safe to monitor without changes in antihypertensive medications. At the initial clinic visit, blood will be collected and stored for analysis. We will measure circulating concentrations of TNF α using the Olink Explore 384 Cardiometabolic panel for this *a priori* specified analysis; this panel will also measure the concentrations of other biomarkers that we will explore further in Exploratory Aims 1 and 2. The Olink analysis uses a Proximity Extension Assay that has been shown to have high specificity and accuracy to allow for assessment of changes in concentrations between repeated samples over time.^{18, 19}

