10.2 Analysis Datasets

These analyses will be conducted as Intention-to-Treat dataset. Per-Protocol Analysis will be explored if electricity monitor data indicates poor compliance with PAC usage (if electricity monitor recordings indicate kilowatt-hour usage that is lower than expected by 50%).

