10.3 Statistical Methods

Aim 1 Analysis.

Descriptive summary statistics, such as mean and standard deviation (or median and inter quartile range) will be reported for continuous variables and counts and proportions for categorical variables. Graphical displays of all variables will be examined, with attention to assessing balance in these characteristics by intervention group, and with assessment of the distribution of variables, relevant to the choice of statistical tests. Statistical comparisons between the PAC and sham groups will be performed using a two-group two-sided t-test or nonparametric Wilcoxon test for continuous variables and Chi-square test for

categorical variables. Distributions of biomarker concentrations will be examined, and non-normally distributed concentrations will be log-transformed, as needed.

The analysis of our primary outcome will use linear mixed-effects models with the change in prespecified biomarker, from pre-intervention to post-intervention, concentrations as the dependent variable and treatment arm as the independent variable. While randomization should obviate the need for additional adjustment, models will be adjusted for age, gender and BMI, as these are known to be related to inflammatory biomarker concentrations.^{20, 21} These models use subject-specific random intercepts to account for heterogeneity between subjects and will account for within subject correlation between biomarker observations. The proposed model is:

$$\Delta TNF\alpha = \beta_1 + \beta_2(PAC\ arm) + \beta_3(age_i) + \beta_4(gender_i) + \beta_4(BMI_i) + e_i$$

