10.4 Sample Size

Power Analysis: While we do not expect substantial participant dropout over this short trial, our power analyses include adjustment for up to 10% dropout in each arm. Based on our meta-analysis of biomarkers²², we estimate a 10% change in concentration of biomarkers with PAC use versus sham.^{13 13} Using a basic multiple regression model incorporating age, BMI, and gender, along with our exposure (active PAC vs sham), we will have greater than 80% power to reject the null hypothesis of zero effect size at the significance level (alpha) of 0.05, with a sample size of 66. As such, our enrollment goal of 44 participants, limited by budgetary constraints, may provide sufficient power to detect significant changes in biomarker concentrations. However, in the event that we are not able to reach statistical significance with the changes we detect, these results will still be informative for developing future studies. We will include baseline-only data for participants who do not complete the protocol.

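### Anyone without a Visit 2 sample drops out of the change-score model, so the promised use of baseline-only data under intention-to-treat is not delivered as written

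*Combined protocol and SAP*

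**What the plan says.** Section 4.1 plans "a total of two time points 4 weeks apart, pre- and post-intervention". The second draw is placed at Visit 2 in section 7.6, four weeks after the air cleaner is switched on: "Collect blood for post-intervention biomarker measurement: <15 mL for all, additional ~10 mL for participants opting into future research". For people who leave, section 7.7 reads "Subjects may withdraw from the study at any time and visit will be scheduled to return any study equipment that has been received". It names the monitors and the data hub and mentions no blood. Section 5.7.2 records the date and reason for withdrawal and rules out replacement.

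Section 4.2.1 defines the primary endpoint as percent change, (post − pre)/pre. Section 10.3 specifies "linear mixed-effects models with the change in prespecified biomarker, from pre-intervention to post-intervention, concentrations as the dependent variable" and writes an equation with arm, age, gender, BMI and a single residual per person. The same section adds "These models use subject-specific random intercepts to account for heterogeneity between subjects" and refers to correlation within a person.

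On who is analysed, section 10.2 states "These analyses will be conducted as Intention-to-Treat dataset", and section 10.4 states "We will include baseline-only data for participants who do not complete the protocol", without a method. Section 5.7.1 says that participants who unexpectedly sleep away for two or more consecutive nights, or seven days in total, must leave the study and that their data will not be analysed. The documents contain no imputation, missing-data assumption or sensitivity analysis for missing TNFα.

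**The concern.** The statements about who is analysed do not fit the model that is to analyse them. A change score exists only for a person with both samples, so a baseline-only participant has nothing to put on the left-hand side of the equation. If the plan is followed as written, the report would call the TNFα comparison intention-to-treat with non-completers included, while the estimate came only from participants with a Visit 2 sample. The Aim 2 model is described as similar and has the same limit.

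Two things are at stake. Outcomes are lost in a small trial, although a 4-week sample could be sought from some of those who leave. The arm contrast may also be biased if the people who leave differ between arms in how their TNFα changed.

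**Working it through.** **1. Who has an outcome.** The outcome for person i is Δᵢ = postᵢ − preᵢ (section 10.3) or 100 × (postᵢ − preᵢ)/preᵢ (section 4.2.1). Both need postᵢ, which comes only from the Visit 2 draw. Without Visit 2, Δᵢ is undefined.

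**2. How many.** Section 10.4 allows up to 10% dropout per arm; section 5.6 expects 90% completion.
- 44 × 0.10 = 4.4, so about 4 lost and about 40 analysed (44 × 0.90 = 39.6).
- 74 × 0.10 = 7.4, so about 7 lost and about 67 analysed (74 × 0.90 = 66.6).

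Both enrolment figures stand in the documents; which is right is a separate matter.

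**3. The plan's own sample size.** Section 10.4 gives 66 for more than 80% power. Dividing by completion, 66/0.90 = 73.3, rounded up to 74, which is the figure in section 5.6. So 66 reads as the number with both samples, and the arithmetic gives people who drop out no contribution.

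**4. What the loss costs in power.** No SD is stated, so 66 cannot be reproduced forward. Back-solving at two-sided 0.05 and 80% power with 33 per arm: d = (1.960 + 0.842) × √(2/33) = 0.69. For a 10-point effect the implied SD is 10/0.69 = 14.5 (14.3 with a t distribution and three covariates). At that inferred SD, power is about 62–63% with 44 analysed and 58–59% with 40. If 66 instead means enrolled (about 60 completing), the implied SD is 13.6–13.8 and the powers are 66–67% and 62–63%. The missing outcomes therefore cost about 4 percentage points.

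**5. Whether the random intercept rescues the sentence in 10.4.** With one Δᵢ per person, the variance is τ² + σ² (subject intercept plus residual). Only the sum can be estimated, because no person contributes a second value to separate the two. The random-intercept wording makes sense only if pre and post values are modelled as two rows per person, which is not the stated dependent variable or equation.

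**6. Numerical check.** I fitted one simulated dataset of 44 participants, 4 without a second sample.
- The change-score regression used 40, and its arm estimate was identical with and without the baseline-only people (−0.352 both times).
- A random intercept added to that regression split the variance arbitrarily into equal halves (0.149 and 0.149).
- A two-time-point model used all 44 people (44 + 40 = 84 rows).

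**7. Bias.** Let p be the missing fraction in an arm and g the difference in mean change between its missing and observed participants. The all-randomised contrast differs from the observed one by p_active × g_active − p_sham × g_sham. The documents give no value for g. As an illustration only, with p = 0.10 in the active arm, g = 5 to 30 points and no such difference in the sham arm, the shift is 0.5 to 3.0 points against a planned 10. With equal p and g in both arms it is zero. At SD 14.4 and 20 per arm the standard error is 14.4 × √(2/20) = 4.6 points, larger than any shift in that range.

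**8. Section 5.7.1 beside section 10.2.** One removes randomised people's data because of something that happened after randomisation; the other says the analysis is by intention-to-treat. Both cannot hold.

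**The case against.** A reader might infer that the plan treats stopping the air cleaner as leaving the study, so that the analysis is confined to adherent completers. The documents do not say this. Section 10.2 sends low electricity use to an additional per-protocol analysis. The post-intervention questionnaire accepts an answer of only a few hours' use a day, and section 7.8 offers a video visit for equipment problems. A low user who attends Visit 2 is sampled and analysed as randomised. The defect is missing outcomes among people who leave.

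Section 10.4 does not say that baseline-only data enter the primary model; they could serve the descriptive summaries. That is possible, but beside an intention-to-treat statement and with no method given, the sentence reads as a promise about the analysis. The random-intercept wording in section 10.3 may also show that a pre/post model was intended. If so, the equation and dependent variable are wrong; the conflict remains either way.

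Some of the few people lost will refuse blood or be unreachable, and consent can be withdrawn, so no draw can be required. Section 10.4 also expects little dropout over four weeks. Both points stand and limit what can be recovered, but they do not make the text consistent.

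**Conclusion.** The point holds as an inconsistency between the stated analysis set and the written model. As written, the primary TNFα analysis contains randomised participants with a Visit 2 sample, whatever their use of the device. The baseline-only people promised in section 10.4 contribute nothing to it: about 4 of 44, or 7 of 74, if dropout reaches the plan's 10%. Section 10.3 contradicts itself on the random intercept, and section 5.7.1 contradicts section 10.2.

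The power loss of about 4 percentage points rests on an SD inferred from the plan's 66. Whether the missing outcomes bias the arm contrast, and by how much, cannot be sized from the documents. A reader might take the illustrative shifts as an estimate; they assume that only one arm loses unusual participants, and similar departures in both arms would cancel.

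**What to change.** 1. In section 10.3, replace the change-score equation with a model of log TNFα at both time points: arm by time with a common baseline mean, a subject random intercept, and age, gender and BMI. Baseline-only participants then enter, and the random-intercept text matches the model. Otherwise, delete the baseline-only sentence in 10.4 and describe the set as randomised participants with a Visit 2 sample.
2. In sections 5.7 and 7.7, seek the scheduled 4-week draw from everyone who leaves or stops use but still agrees, and analyse them as randomised. An earlier sample, for instance at equipment return, does not measure a 4-week change; flag it by its timing and use it only in a sensitivity analysis.
3. Reconcile the data exclusion in 5.7.1 with the intention-to-treat statement in 10.2.

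Cost: mostly wording, since two samples per participant are already planned, but it needs an IRB-approved amendment (section 13.2). Some recovered samples will be off-treatment, and not everyone who leaves will agree to a draw. Baseline-only rows add little information on the arm difference, so obtaining the 4-week sample matters more than the change of model.

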7.8 Unscheduled Visit

Participants may request an unscheduled video visit to troubleshoot equipment-related issues if needed.

8 Assessment of Safety

This study involves the use of commercially available products associated with no known risks to consumers. The Principle Investigator and Co-Investigator, [name], will monitor data safety of the overall study. We will review safety events related to blood pressure monitoring and blood draws at weekly team meetings with biweekly participant reviews complied by study coordinators. Given the established safety of all commercially available equipment used in this protocol, there are no predefined stopping rules for the study (no superiority/futility). After data safety assessments, study team will be notified via email of any changes in protocol.

9 Clinical Monitoring

Clinical site monitoring is conducted to ensure that the rights and well-being of human subjects are protected, that the reported trial data are accurate, complete, and verifiable, and that the conduct of the trial follows the currently approved protocol/amendment(s), and with applicable regulatory requirement(s). This is a single-site study; data, training, procedures, and practices will be monitored continuously throughout the study period by study PIs. A quality management plan will be developed if needed.

10 Statistical Considerations

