2.3 Potential Risks & Benefits

2.3.1 Known Potential Risks

This is a minimal risk study, with no physical risks associated with the study design. Potential minimal risks are as follows:

(1) **Risk of PAC use:** In our published review of the effect of personal air cleaners (PACs) on blood pressure control, no risks were reported.¹² While it is possible that use of a PAC might disrupt sleep, it is unlikely. In fact, frequently PACs have been used to generate “white noise” associated with improved sleep latency and duration in a variety of settings.

(2) Risk of monitoring air pollution: There are no known risks to participants with monitoring the amount of air pollution exposure. At conclusion of the 3-month study, data on air pollution exposure will be provided to study participants. There is no risk to participants in ongoing air pollution exposure during this time interval.

(3) Risk of blood collection. There are minimal risks associated with a standardized venipuncture for blood collection. These risks include pain, discomfort and superficial bleeding or bruising. All participants in the clinical cohort will provide consent for standard blood collection, in which these minimal risks will be described. For participants in the clinical cohort, up to <15 mL (≈ 1 tablespoons and $\approx 3\%$ of a standard blood donation) of blood will be collected at the baseline visit and 4-week visit. The total amount of blood collected will be <30 mL for the main study. For participants opting into biospecimen storage, an additional ≈ 10 mL will be drawn at each visit for a total of <50 mL for the entire study. This presents minimal risk to study participants.

(4) Risk of monitoring home blood pressure and ambulatory blood pressure. There are no known direct risks to participants associated with the use of home blood pressure monitors or ambulatory monitors. These devices are routinely prescribed for self-monitoring and clinician-assisted decision making for hypertension. There is a potential risk of increased anxiety due to self-monitoring of blood pressure. Study coordinators will discuss any concerns regarding home blood pressure monitoring at video visit with study participants and will refer any concerns on recorded blood pressure values to participants' managing physician.

(5) Risk of discomfort with staff visualizing participants' homes during video visit for equipment setup

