- 2. On average, how much time did you run the filter each day?
 - a. I kept it on for 24 hours a day
 - b. I ran it for most of the day (18-24 hours)
 - c. I ran it for more than half of the day (12-18 hours)
 - d. I ran it for part of the day (6-12 hours)
 - e. I ran it for a few hours (0-6 hours)
- 3. How much did you notice noise from the filter?
 - a. Extremely noisy
 - b. Very noisy
 - c. Somewhat noisy
 - d. Minimal noise
 - e. I didn't hear it at all
- 4. How likely is it that you will buy replacement filters in the future? [Likert scale]
 - a. Very likely
 - b. Somewhat likely
 - c. Not very likely
 - d. Not likely at all
- 5. *[If less than very likely....]* What are some of the reasons why you might not buy replacement air filters (check all that apply)?
 - a. Too costly
 - b. Too inconvenient
 - c. Don't know where to buy them
 - d. Too noisy

- e. Not sure they are effective
- f. Other: _____

6. During the study period did you have a change in your blood pressure medication?

- a. Yes
- b. No
- c. Don't know/refused

7. How concerned are you about the effects of air pollution on your health?

- a. Very concerned
- b. Somewhat concerned
- c. Not very concerned
- d. Not concerned at all

8. Would you be interested in continuing to participant in this study and check your BP twice daily for 3 months?

- a. Yes
- b. No
- c. Don't know/refused

9. If this study continued for 6 months, would you be interested in continuing to participate and check your BP daily?

- a. Yes
- b. No
- c. Don't know/refused

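### The air cleaner is outside the stated safety review, and no scheduled contact after setup asks about sleep or monitoring concerns, so these harms may be under-ascertained

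*Combined protocol and SAP*

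**What the plan says.** Section 2.3.1 names two harms that could arise during the four weeks. The first concerns the device: "While it is possible that use of a PAC might disrupt sleep, it is unlikely". The second concerns home readings: "There is a potential risk of increased anxiety due to self-monitoring of blood pressure". For the second it gives a response: "Study coordinators will discuss any concerns regarding home blood pressure monitoring at video visit with study participants".

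Section 8 describes the ongoing review: "We will review safety events related to blood pressure monitoring and blood draws at weekly team meetings", and the sentence goes on "with biweekly participant reviews complied by study coordinators". It also makes two investigators responsible for data safety across the study, and it justifies a light plan by the established safety of the equipment.

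Section 7.5 gives the purpose of the video visit: "Conduct video visit at a mutually agreeable time to instruct participants in equipment setup". Its one blood pressure item is "Supervise participant self-measuring BP once to ensure real-time data transmission". Section 7.6 (Visit 2) lists equipment return and blood collection. Section 7.8 allows extra video visits on request, for equipment problems.

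Section 14.1 has adverse events and expected adverse reactions entered in RedCAP, with no restriction by cause. The post-intervention part of Attachment A asks "How much did you notice noise from the filter"; it has no item on sleep or anxiety.

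**The concern.** The review is defined by a list of two sources of events, and the list leaves out the thing being randomised. The cleaner runs 24 hours a day in the bedroom for four weeks (Section 6.1.4), and its one named harm concerns sleep. Planned discussion of monitoring concerns falls at setup, before the weeks of twice-daily readings that could cause anxiety.

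What is at stake is how a quiet safety record would be read. Section 2.3.1 already relies on a published review in which no risks of air cleaners were reported. This trial could add a second statement of that kind when participants had not been asked about the named harm and the review was not directed at the device. The efficacy analysis of TNFα is untouched.

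**Working it through.** The plan gives no figure to reproduce. The check is to set the sections side by side and ask, for each named harm, whether it is reviewed, asked about, recorded and summarised.

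| Step | Sleep disruption (air cleaner) | Anxiety (self-monitoring) |
|---|---|---|
| Named as a possible harm (2.3.1) | Yes | Yes |
| Within the weekly review (8) | No: only blood pressure monitoring and blood draws are listed | Yes: it is an event related to blood pressure monitoring |
| Discussed at the setup video visit (2.3.1, 7.5) | Not mentioned | Yes, before most of the exposure |
| Explicitly asked about at Visit 2 (7.6) | No | No |
| Asked in the post-intervention questionnaire (Attachment A) | No; noise only | No |
| Recorded if volunteered (14.1) | Yes | Yes |
| Summarised in the analysis (10) | No | No |

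**Time without a scheduled question.** Visit 2 is four weeks after the cleaner is switched on, and the final draw may be up to 35 days after (Section 7.6). No participant contact is scheduled between setup and Visit 2.

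**The biweekly participant reviews (Section 8).** They recur, but their content is not stated. Nothing says that participants are questioned for them, and they feed a review whose listed scope omits the cleaner.

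**The questionnaire.** Section 7.6 does not list it as a Visit 2 procedure, and Section 19 says the attachments are not part of the protocol. Noise is a partial indicator of tolerability and does not measure sleep.

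**The analysis section.** The descriptive summaries in Section 10.3 concern distributions and balance between arms. Adverse events are not mentioned anywhere in Section 10.

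**Illustration of what asking would buy.** If every exposed participant is asked and none reports the event, the exact one-sided 95% upper limit on the event rate is 1 − 0.05^(1/n). Both arms run the same model, described as identical in sound (Sections 4.1 and 6), so both are exposed to a running device in the bedroom.

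- n = 44 (Sections 5.4 and 10.4): 1 − 0.05^(1/44) = 0.066, or 6.6%.
- n = 40, after about 10% dropout (44 × 0.9 = 39.6): 1 − 0.05^(1/40) = 0.072, or 7.2%.

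Sections 4.1 and 5.6 give 74 participants instead of 44. With n = 74 the limit would be 1 − 0.05^(1/74) = 0.040, or 4.0%. If participants are not asked, zero reports give no limit at any n.

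**The case against.** A reader might infer that both named harms would go unreported. The documents do not support that:

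- Anxiety caused by self-monitoring is an event related to blood pressure monitoring, so the weekly review covers it.
- Section 14.1 records adverse events of any cause, so a volunteered sleep complaint would be captured. Section 5.7.2 also records reasons for withdrawal.
- Coordinators' biweekly participant reviews and the investigators' overall responsibility continue after setup. Follow-up cannot be said to end at day 0.
- A post-intervention questionnaire exists, so the bullets in Section 7.6 may not be everything asked at the end.

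These points stand, and they limit the conclusion to possible under-ascertainment. They do not close the gap: a storage rule does not say who asks or when, the content of the biweekly reviews is unspecified, and the questionnaire has no item on either harm.

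A reader might also compute the zero-event limit from the active arm alone: 12.7% for 22 participants, 13.9% for 20. That is the wrong denominator for disruption by a running device, because the sham runs too.

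It is also fair to say that the plan calls sleep disruption unlikely, that this is a minimal-risk study of a consumer product, and that no objective or endpoint concerns device safety. That keeps the severity low. It does not explain why the study device is left out of a review that already meets weekly.

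**Conclusion.** The point holds as a minor one. Sleep disruption from the air cleaner is outside the stated review and is not asked about at any scheduled contact. Anxiety from self-monitoring is inside the review but is not explicitly asked about after setup. Neither harm has a planned summary. Both may be under-ascertained, to an extent that the documents do not allow one to estimate.

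This rests on reading Section 8's list as the scope of the review and on the biweekly reviews containing no direct questions on these harms. If they do contain such questions, stating so would settle the elicitation part. The 6.6% and 7.2% limits are illustrative: they assume systematic asking, no events, and both arms exposed. No efficacy result changes.

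**What to change.** Reconcile Section 8 with Sections 2.3.1 and 14.1:

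1. In Section 8, add events related to the air cleaner to the existing weekly review.
2. In Section 7.6, have the coordinator ask about sleep and about monitoring concerns at Visit 2. Alternatively, add both items to the post-intervention questionnaire; under Section 19 an attachment can be changed without a protocol amendment.
3. In Section 10, tabulate by arm the adverse events recorded in RedCAP and the Attachment A noise item. Because both arms run a device, give the pooled column too. The noise item by arm also bears on the statement that active and sham units sound identical.
4. Do not claim an absence of device harms from volunteered reports alone.

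The cost is wording in a few sections, about a minute of coordinator time at a visit that already exists, and one descriptive table. No new visit, staff or procedure is needed, and no clinical rule is set.
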